Appendix 3. Ann Arbor Lymphoma Staging System

Area of Involvement	Stage
Single lymph node group or lymph node region	1
Two or more node regions on same side of diaphragm	2
Lymph node regions on both sides of the diaphragm	3
Multiple extra-nodal sites or lymph nodes and extra-nodal sites	4

Additional Anatomic Factors	Designation
Confined to lymph nodes	N
Site of bulky disease (> 10 cm in diameter)	X
Extra-nodal extension or single isolated site of extra-nodal disease	E
Hepatic	H
Lung	L
Bone marrow	M
Spleen	S
Pleura	P
Bone	O
Skin	D

Additional Symptomatic Factors	Designation
No symptoms	A
Symptoms of weight loss > 10% within 6 months, fever, night sweats	B

Appendix 4. Pregnancy Precautions, Definition for Female of Childbearing Potential, and Contraceptive Requirements

1) Definitions

a. Definition of Childbearing Potential

For the purposes of this study, a female born subject is considered of childbearing potential following the initiation of puberty (Tanner stage 2) until becoming postmenopausal unless the subject is permanently sterile or has medically documented ovarian failure.

Women are considered to be in a postmenopausal state when they are ≥ 54 years of age with cessation of previously occurring menses for ≥ 12 months without an alternative cause. In addition, women of any age with amenorrhea of ≥ 12 months may also be considered postmenopausal if their follicle-stimulating hormone level is in the postmenopausal range and they are not using hormonal contraception or hormonal replacement therapy.

Permanent sterilization includes hysterectomy, bilateral oophorectomy, or bilateral salpingectomy in a female subject of any age.

a) Definition of Male Fertility

For the purposes of this study, a male born subject is considered fertile after the initiation of puberty unless the subject is permanently sterile by bilateral orchidectomy or medical documentation.

2) Contraception Requirements for Female Subjects

a. Study Drug Effects on Pregnancy and Hormonal Contraception

Idelalisib is contraindicated in pregnancy as a malformation effect has been demonstrated/suspected or is unknown taking into consideration class effects, genotoxic potential, or a strong suspicion of human teratogenicity/fetotoxicity in early pregnancy based on nonclinical data. Idelalisib has demonstrated/suspected or has insufficient data to exclude the possibility of a clinically relevant interaction with hormonal contraception that results in reduced contraception efficacy. Therefore, contraceptive steroids are not recommended as a contraceptive method either solely or as a part of a contraceptive regimen. Please refer to the latest version of the investigator's brochure for additional information.

b. Contraception Requirements for Female Subjects of Childbearing Potential

The inclusion of female subjects of childbearing potential requires the use of highly effective contraceptive measures with a failure rate of $< 1\%$ per year. They must also not rely on hormonal contraceptives as a form of birth control during the study. They must have a negative serum pregnancy test at screening and a negative pregnancy test on Day 1 prior to randomization. Pregnancy tests will be performed at monthly intervals thereafter until the end of contraception requirement.

Duration of required contraception for female subjects in this clinical trial should start from the Screening visit until 30 days post last dose of study drug.

Female subjects must agree to use 1 of the following contraceptive methods:

Complete abstinence from intercourse of reproductive potential. Abstinence is an acceptable method of contraception only when it is in line with the subject's preferred and usual lifestyle.

Or

Consistent and correct use of 1 of the following methods of birth control listed below:

- Non-hormonal intrauterine device (IUD)
- Bilateral tubal occlusion (upon medical assessment of surgical success)
- Vasectomy in the male partner (upon medical assessment of surgical success)

Inclusion of methods of contraception in this list of permitted methods does not imply that the method is approved in any country or region. Methods should only be used if locally approved.

Female subjects must also refrain from egg donation and in vitro fertilization during treatment and until the end of contraception requirement. If needed, female subjects should be advised to seek advice about egg donation and cryopreservation of germ cells prior to treatment.

3) Contraception Requirements for Male Subjects

It is theoretically possible that a relevant systemic concentration of study drug may be achieved in a female partner from exposure to the male subject's seminal fluid and poses a potential risk to an embryo/fetus. Therefore, male subjects with female partners of childbearing potential must use condoms during treatment until 90 days after last dose of study drug. If the female partner of childbearing potential is not pregnant, use of locally approved contraceptive methods should also be considered.

Male subjects must also refrain from sperm donation during treatment and until the end of contraception requirement.

4) Unacceptable Birth Control Methods

Birth control methods that are unacceptable include periodic abstinence (eg, calendar, ovulation, symptothermal, postovulation methods), withdrawal (coitus interruptus), spermicides only, and lactational amenorrhea method. A female condom and male condom should not be used together.

5) Procedures to be Followed in the Event of Pregnancy

Female subjects will be instructed to notify the investigator if they become pregnant or suspect they are pregnant at any time from start of the study to 30 days post last study drug dose. Study drug must be discontinued immediately.

Male subjects whose partner has become pregnant or suspects she is pregnant from start of study to 90 days post last study drug dose must also report the information to the investigator. Instructions for reporting pregnancy, partner pregnancy, and pregnancy outcome are outlined in Section [7.6.2.1](#).

Appendix 5. Follicular Lymphoma International Prognostic Index

Follicular Lymphoma International Prognostic Index (FLIPI) Scoring System

Parameter	Value	Point Score
Age	> 60 years of age	1
Ann Arbor stage	Stage III or IV	1
Hemoglobin level	< 120 g/L (12.0 g/dL or 6.37 mmol/L)	1
Serum LDH	> ULN	1
Number of Nodal Sites	> 5	1

Risk Group by FLIPI Total Point Score

Risk Group	Total Point Score
Low	≤ 1
Intermediate	2
High	≥ 3

{Mills 2012}

Appendix 6. Efficacy Assessments

Tumor Status Assessments

The determination of lymphoma response and progression will be based on standardized criteria {Cheson 2007} as specifically modified for this study to reflect the biology of the diseases under study and the pharmacology of idelalisib and the methods to be used in evaluation. During the course of the study, investigators will periodically assess the status of each subject's lymphoma. If progression is suspected, the IRC will be notified and will review radiographic and pertinent clinical data in order to provide expert interpretation. Treatment decisions by the investigator in this study will be based, in part, on these assessments. The findings of the IRC will be considered primary for analyses of ORR and other tumor control endpoints.

Method of Assessment

In addition to clinical examination, imaging-based evaluation will be used in this study in all subjects enrolled. CT scan is the preferred method for radiographic tumor assessment. MRI scanning may be used at the investigator's discretion in subjects for whom this may be a preferred alternative to CT scanning; however, if MRI is performed, a non-contrast CT of the chest should also be performed. Contrast-enhanced scanning is preferred, but contrast material may be omitted in subjects for whom use of a contrast agent would be medically contraindicated. If available, PET scan data will be considered in response and progression assessment; however, PET scanning will not be a required component of assessment in this study. As appropriate, study treatment dosing delays, bone marrow aspirate/biopsy information (eg, for confirmation of CR) and lymph node biopsy information (eg, for documentation of disease transformation to an aggressive histology) will also be considered.

For radiographic assessments, the same method of assessment and the same technique (eg, scan type, scanner, subject position, dose of contrast, injection/scan interval) should be used to characterize each identified and reported lesion at baseline, while on study drug treatment and during the open-label extension. Furthermore, the use of intravenous (IV) contrast should be consistent across time points. In the event that the screening/baseline CT scan of the neck, chest, abdomen, and pelvis is performed without IV contrast, follow-up time points should also be performed without IV contrast.

All relevant radiographic and clinical information required to make each tumor status assessment must be made available for source verification and for submission to the IRC.

Timing of Assessments

During screening, clinical and imaging-based tumor assessments should be performed within the specified screening period. On-study PET-CT/CT/MRI tumor assessments should be performed at as indicated in [Appendix 2](#). An end-of-study PET-CT/CT/MRI tumor assessment should be performed unless the subject already has radiographic confirmation of disease progression ≤ 4 weeks prior to study discontinuation. If a subject permanently discontinues study drug prior to objective documentation of lymphoma progression, investigators should continue further follow-up until lymphoma progression is documented by the IRC.

Timing of Assessments – Subjects enrolled Prior to Protocol Amendment 5

Subjects randomized to 100 mg twice daily idelalisib with SD or PD will be unblinded and dose escalated to 150 mg twice daily. Subjects randomized to 150 mg with SD will be unblinded. The subjects should continue PET-CT/CT/MRI tumor assessments as indicated in [Appendix 2](#), until lymphoma progression is documented by the IRC. Subjects with PD on the 150 mg twice daily arm will be discontinued from study.

Identification and Follow-up of Tumor Lesions and Organomegaly

Index Lesions

Up to 6 lesions (eg, lymph nodes, liver or spleen nodules, and/or other circumscribed extra-nodal masses) should be selected as index lesions that will be used to quantitate the status of the disease during study. Ideally, the index lesions should be located in disparate regions of the body and include mediastinal, abdominal, and retroperitoneal areas of disease whenever these sites are involved.

Index lesions will be measured and recorded at baseline and at the stipulated intervals. The cross-sectional dimensions (the largest cross-sectional diameter, ie, the longest diameter [LD] × the longest perpendicular diameter [LPD]) will be recorded (in cm) for each index lesion. Using the LD and LPD, the product of the perpendicular diameters (PPD) for each index lesion will be calculated. The sum of the products (SPDs) for all index lesions will be calculated and recorded. The baseline SPDs will be used as references by which objective tumor response will be characterized during treatment. The nadir LDs of individual lesions and the nadir SPDs will be used as references by which objective tumor progression will be characterized during study. All PPD and SPD measurements will be reported in centimeters squared.

Nodal Index Lesions

A nodal mass may be selected as a nodal index lesion if it is both abnormal and measurable at baseline. A lymph node lesion is considered abnormal if it has a single diameter >1.5 cm regardless of the LPD. If a lymph node lesion has a LD of 1.1 to 1.5 cm it should only be considered abnormal if its LPD is more than 1.0 cm.

Abnormal, measurable nodal lesions will be subcategorized as either large or small.

- Large nodal lesions have an LD that is > 1.5 cm and an LPD that is ≥ 1.0 cm.
- Small nodal lesions have an LD that is > 1.0 cm and ≤ 1.5 cm and an LPD that is > 1.0 cm.

Index lesions measuring > 1.5 cm in the LD, regardless of the measurement of the LPD, will be prioritized during baseline index lesion selection.

At follow-up time points, the SPD of all nodal index lesions will be considered. Because nodal index lesions that have one or both diameters > 0 cm and < 1.0 cm cannot be reliably measured, a default value of 1.0 cm will be assigned for each diameter that meets these criteria and the resulting PPD will be used in SPD calculations. Based on this convention, a CR may be achieved even if an SPD value is > 0 cm² (ie, if all lymph nodes measure ≤ 1.0 cm²).

New or enlarging nodal lesions that are still ≤ 1.0 cm by ≤ 1.0 cm will not be considered to represent recurrent disease or PD. A new node that measures > 1.5 cm in any diameter or a new node that measures > 1.0 cm to ≤ 1.5 cm in the LD and measures > 1.0 cm in the LPD will be considered PD.

In cases in which a large lymph node mass has split into multiple components, only those elements that are > 1.0 cm in at least 1 diameter will be considered abnormal and used in calculating the SPD. Components that are ≤ 1.0 cm in the LD are assumed to be normal lymph node structures. PD will not be based on the growth of a lesion sub-component until it meets the criteria for abnormal. Lesion sub-components that are abnormal (> 1.0 cm in ≥ 1 diameter) will have the true PPDs calculated with the result used only for calculating an accurate nadir. Lesion sub-components that are normal (≤ 1.0 cm in the LD) will have the default PPD of 1.0 cm² (1.0 cm x 1.0 cm) stored only for the purposes of calculating the nadir value.

If lesions merge, a boundary between the lesions will be established so the LD of each individual lesion can continue to be measured. If the lesions have merged in a way that they can no longer be separated by this boundary, the newly merged lesion will be measured bi-dimensionally.

Extra-Nodal Index Lesions

An extra-nodal mass may be selected as an index lesion if it is both abnormal and measurable at baseline. An extra-nodal mass of any size is considered abnormal. It is considered measurable at baseline if it has 2 perpendicular diameters that can be accurately measured in cross section with the LD being ≥ 1.0 cm and the LPD also being ≥ 1.0 cm.

At follow-up time points, the PPD of each single extra-nodal index lesion and the SPD of all extra-nodal index lesions will be considered. Because extra-nodal index lesions that have one or both diameters > 0 cm and < 1.0 cm cannot be reliably measured, a default value of 1.0 cm will be assigned for each diameter that meets these criteria and the resulting PPD will be used in SPD calculations. If an extra-nodal lesion is no longer clearly visible, it will be considered resolved and its PPD will be defined as 0 cm².

If an extra-nodal lesion that had resolved (ie, had a PPD of 0 cm²) subsequently reappears unequivocally, the subject will be considered to have PD. A new unequivocal extra-nodal lesion of any size that appears at a site that was not previously involved with lymphoma and is discernible to the radiologist by CT scan will be considered PD.

Non-Index Lesions

Any other measurable and abnormal nodal or extra-nodal lesions not selected for quantitation as index lesions may be considered non-index lesions. In addition, non-measurable evidence of lymphoma such as abnormal, non-measurable nodal lesions, extra-nodal lesions with both diameters < 1.0 cm, bone lesions, leptomeningeal disease, ascites, pleural or pericardial effusions, lymphangitis of the skin or lung, abdominal masses that are not confirmed and followed by imaging techniques, cystic lesions, previously irradiated lesions, or lesions with artifacts may be considered as non-index disease.

If present at baseline, up to 6 non-index lesions should be recorded. Measurements are not required.

Non-index disease will be used as a general reference to further characterize regression or progression of lymphoma during assessments of the objective tumor response during treatment. These lesions should be followed as “present”, “absent” or “progressed.”

Spleen and Liver

Qualitative assessments of the sizes of the spleen and liver will be performed. In addition, the presence or absence of splenic and/or hepatic nodules will be recorded.

Bone Marrow

Bone marrow assessments will be based on morphologic evaluation of bone marrow biopsies. Immunohistochemistry may be used to assess response if the sample is indeterminate by morphology.

In a subject who has a baseline bone marrow biopsy showing bone marrow lymphoma or does not have a baseline bone marrow examination, declaration of an on-study CR requires bone marrow biopsy documentation of the absence of bone marrow lymphoma. In a subject who has a baseline bone marrow biopsy showing no evidence of lymphoma, declaration of an on-study CR does not require bone marrow examination as long as other criteria for CR are met.

Biopsy and Cytology

During study participation, a subject who has a biopsy or cytology indicating a new site of disease or transformation to an aggressive lymphoma will be considered to have PD even in the absence of other evidence of PD. If the subject has no earlier objective documentation of PD, the date of the biopsy or cytology will be considered the date of lymphoma progression.

Definitions of Tumor Response and Progression

Responses will be categorized as complete response (CR), very good partial response, partial response (PR), stable disease (SD), or progressive disease (PD). In addition, a response category of not evaluable (NE) is provided for situations in which there is inadequate information to otherwise categorize response status. A response category of no disease (ND) is included for situations in which there is no evidence of tumor both at baseline and on-treatment.

The best overall response will be determined. The best overall response is the best response recorded from the start of study drug until PD/recurrence (taking as reference for PD the smallest measurements recorded since study drug started). Subjects with a best overall response of NE or ND will be included in the denominators in calculations of tumor response rate.

Response Categories

Complete Response

To satisfy criteria for CR, all of the following criteria must be met:

- No evidence of new disease
- Regression of all index nodal lesions to normal size (≤ 1.5 cm in the LD for nodes that were considered large at baseline and ≤ 1.0 cm in the LD and ≤ 1.0 cm in the LPD for nodes that were considered small at baseline) Regression to normal of all nodal non-index disease
- Disappearance of all detectable extra-nodal index and non-index disease
- Normal spleen and liver size by imaging studies, no hepatic or splenic lymphoma nodules, and no new liver or spleen enlargement
- Morphologically negative bone marrow based on an adequate unilateral core biopsy (> 20 mm unilateral core); if the sample is indeterminate by morphology, it should be negative by immunohistochemistry. After the subject meets radiographic CR, the window for bone marrow biopsy is within 30 days from the date that CR was met.
- If PET performed (not required), no evidence of residual disease

Partial Response

To satisfy criteria for PR, all of the following criteria must be met as noted below:

- No evidence of new disease
- A $\geq 50\%$ decrease from baseline in the SPD of the index lesions
- No increase in the size of non-index disease

- No increase in the size of the liver or spleen and no new liver or spleen enlargement
- Persistence of bone marrow involvement in a subject who meets other criteria for CR based on the disappearance of all nodal and extra-nodal masses
- If PET performed (not required):
 - Typically fluorodeoxyglucose (FDG)-avid lymphoma: if no baseline PET scan or if the PET scan was positive before initiating study drug(s), the on-treatment PET is positive in ≥ 1 previously involved site. If baseline PET was performed and was negative, there is no new PET evidence of disease
 - Variably FDG-avid lymphoma/FDG-avidity unknown: if no pretreatment PET scan or if the pretreatment PET scan was negative for lymphoma, CT criteria should be used in assessing the tumor during study. If the PET scan was positive before initiating study drug(s), the on-treatment PET is positive in ≥ 1 previously involved site.

Stable Disease

To satisfy criteria for SD, all of the following criteria must be met:

- No evidence of new disease
- Neither sufficient tumor shrinkage from baseline to qualify for PR nor sufficient evidence of tumor growth to qualify for PD

Progressive Disease

The occurrence of any of the following events indicates progressive disease (PD):

- Evidence of any new disease that was not present at baseline:
 - A new node that measures > 1.5 cm in LD and > 1.0 cm in the LPD.
 - A new node that measures > 1.0 cm to ≤ 1.5 cm in the LD and > 1.0 cm in the LPD
 - Unequivocal reappearance of an extra-nodal lesion that had resolved (ie, had previously been assigned a PPD of 0 cm²)
 - A new unequivocal extra-nodal lesion of any size
 - New non-index disease (eg, effusions, ascites, or other organ abnormalities) of any size unequivocally attributable to lymphoma (usually requires PET, biopsy, cytology, or other non-radiologic confirmation to confirm disease attributable to lymphoma).
- Note: Isolated new effusions, ascites, or bone lesions are not sufficient evidence alone of PD unless histologically confirmed. In subjects with no prior history of pulmonary lymphoma, new lung nodules identified by CT are usually benign. Thus, a declaration of PD should not be made if this is the only manifestation of an apparently new lesion.***

- New or recurrent bone marrow involvement with lymphoma if the last prior bone marrow biopsy performed as part of the study (baseline or on-study) was negative for lymphoma
- Evidence of worsening of nodal or extra-nodal index lesions:
 - Increase from the nadir by $\geq 50\%$ in the SPD of index lesions
 - Increase from the nadir by $\geq 50\%$ in the LD of an individual node or extra-nodal mass that now has an LD of > 1.5 cm and an LPD of > 1.0 cm
- Unequivocal increase in the size of non-index disease
- Transformation to a more aggressive NHL histology as established by lymph node biopsy
- If PET performed (not required):
 - The appearance of any new lesion compatible with lymphoma with confirmation by other radiographic or histological modalities
 - The reappearance of any activity in a pre-existent lesion that meets size criteria for a new lesion on CT

Note: If there is uncertainty regarding whether there is definitive lymphoma progression, the subject should continue study drug(s) and remain under close observation (eg, evaluated at scheduled intervals) pending confirmation of progression status by the IRC. In particular, worsening of constitutional symptoms in the absence of objective evidence of worsening lymphoma will not be considered definitive disease progression; in such subjects, both lymphoma-related and non-lymphoma-related causes for the constitutional symptoms should be considered. Transient worsening of disease during temporary interruption of study drug(s) (eg, for intercurrent illness) may also not indicate definitive disease progression. In these instances, PET-CT/CT/MRI should be attempted in order to document whether definitive disease progression has occurred. If subsequent evaluations suggest that the subject has experienced persistent definitive disease progression, then the date of progression will be the time point at which progression was first objectively documented.

Non-Evaluable

In a subject who does not have evidence of PD, the occurrence of any of the following conditions indicates a response status of NE:

- There are no images or inadequate or missing images.

Note: A time-point will be considered to have a response of NE if any index lesion is missing. PD may be assigned at any time point regardless of the extent of missing index or non-index lesions. Missing non-index lesions will not impact the ability to assess for response or disease progression.

No Disease

In a subject who does not have evidence of PD, the occurrence of all of the following conditions indicates a response status of ND:

- Index disease absent at both baseline and on-study.
- Non-index disease absent at both baseline and on-study.
- Enlargement of the liver and spleen absent at both baseline and on-study.

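### Under Protocol Appendix 6 a PET-negative subject with a ≥50% SPD fall and a residual node above 1.5 cm is neither CR nor PR, and the new-node progression wording differs between two places

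*Protocol*

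**What the plan says.** **Response (Protocol Appendix 6, Response Categories).**
- PR requires every listed criterion, including a fall of at least 50% in the SPD of the index lesions. Its PET item applies only if PET was done. For typically FDG-avid lymphoma it reads "if no baseline PET scan or if the PET scan was positive before initiating study drug(s), the on-treatment PET is positive in" at least one previously involved site. For variably avid lymphoma it reads "if the PET scan was positive before initiating study drug(s), the on-treatment PET is positive in" at least one such site.
- CR requires index nodes that were large at baseline to come down to an LD of 1.5 cm or less. A clean PET, if done, is a further condition and does not replace the size limit.
- SD requires no new disease, too little shrinkage for PR and too little growth for PD.
- A very good partial response is named among the categories but never defined.

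**New nodes (same Appendix).** Under Nodal Index Lesions, PD includes "A new node that measures > 1.5 cm in any diameter". The Progressive Disease list has instead "A new node that measures > 1.5 cm in LD and > 1.0 cm in the LPD". Both give the same rule for nodes with LD above 1.0 and up to 1.5 cm. The Appendix's baseline definition is "A lymph node lesion is considered abnormal if it has a single diameter >1.5 cm regardless of the LPD".

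**Context.** PET is optional but is considered when available (Appendix 6, Method of Assessment), and PET-CT is an allowed modality (Protocol 6.1.7). SAP section 6 refers to the published 2007 criteria and does not mention the study-specific modifications in Appendix 6. SAP section 1 gives SAP methods precedence over the protocol.

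**The concern.** The PET rule runs the wrong way. Two subjects with the same CT shrinkage are classified differently, and the one whose PET has turned negative does worse than one with no PET or with a PET that is still positive. The category decides membership of the ORR numerator, a primary endpoint assessed by the IRC.

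If the IRC put such a subject in SD by default, treatment could also have changed. Before Amendment 5, IRC-assessed SD at Week 8 led to unblinding and, in the 100 mg arm, to optional escalation (Protocol 3.2.2).

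The new-node wording matters because IRC progression ends study drug (Protocol 3.5.1) and dates the PFS and DOR events. Absence of new disease is also a condition for CR, PR and SD. A progression date should not depend on which part of the Appendix a reader applies.

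**Working it through.** **1. The plan's own figure.** With n = 120 and true ORR 56% (Protocol 8.8), P(X ≥ 60) = 0.921, which reproduces the stated 92%. That figure is not in dispute; it rests on how a responder is defined.

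**2. Applying the CR and PR lists as written.** Take one index node, large at baseline, of 6 × 4 cm (24 cm²) that shrinks to 2.0 × 1.5 cm (3 cm²). The SPD change is 1 − 3/24 = 87.5%. Assume no new disease and that the remaining CR and PR conditions are met.

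| Baseline PET | On-treatment PET | Residual LD > 1.5 cm | Residual LD ≤ 1.5 cm |
|---|---|---|---|
| any | not done | PR | CR |
| positive | positive | PR | PR |
| positive | negative | neither CR nor PR | CR |
| negative | negative | PR | CR |

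The third row is the same in both avidity branches. In the typically avid branch it also arises with no baseline PET and a negative on-treatment PET, although follow-up by a single modality (Protocol 3.2) should make that rare.

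No remaining category clearly fits the third row. SD presupposes too little shrinkage for PR, and 87.5% is well past 50%. Not evaluable needs missing or inadequate images. No disease needs absence of disease at baseline. Very good partial response has no definition.

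**3. New-node wording.**

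| LD × LPD (cm) | Area (cm²) | Nodal Index Lesions | Node items of the PD list |
|---|---|---|---|
| 1.1 × 1.1 | 1.21 | PD | PD |
| 1.6 × 1.0 | 1.6 | PD | not listed |
| 2.0 × 0.9 | 1.8 | PD | not listed |
| 3.0 × 1.0 | 3.0 | PD | not listed |
| 2.0 × 1.1 | 2.2 | PD | PD |

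The texts differ only at LD > 1.5 cm with LPD ≤ 1.0 cm. A reader using the node items of the PD list alone would call the 1.21 cm² node PD and not the one 3.0/1.21 = 2.5 times its area.

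**4. Possible date shift.** This applies if such a node is the only new finding and PD is otherwise first called at the next scheduled scan (Protocol 6.1.7).
- Enrolled as of Amendment 5 (Weeks 12, 24, 36, 48, 60, 84): gaps of 12 weeks, then 24.
- Enrolled before it (Weeks 8, 16, 24, 36, 48, 60, 84): gaps of 8, 8, 12, 12, 12 and 24 weeks.

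**5. Effect on ORR.** One subject is 100/120 = 0.83 points or 100/26 = 3.85 points. The documents do not give the final n. The 26 is the approximate enrolment per arm before Amendment 5 (Protocol 4.1). Starting counts are set near 56% (0.56 × 120 = 67.2; 0.56 × 26 = 14.6), and the numbers of subjects lost are assumptions. Intervals are Clopper-Pearson 95%.
- n = 120: 67 responders, 55.8% (46.5–64.9); one lost, 66, 55.0% (45.7–64.1); three lost, 64, 53.3% (44.0–62.5).
- n = 26, starting at 14: 53.8% (33.4–73.4); one lost, 13, 50.0% (29.9–70.1); two lost, 12, 46.2% (26.6–66.6).
- n = 26, starting at 15: 57.7%; two lost, 13, 50.0%.

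**The case against.** **The PR list is not meant literally.** Its marrow item, "Persistence of bone marrow involvement in a subject who meets other criteria for CR", cannot be required of every PR, so the list has to be read conditionally. That is right, but the PET item states its own conditions (PET done, baseline positive), and the affected subjects meet exactly those.

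**The gap grades the subject SD.** A reader might infer that such a subject is SD at best. The SD wording does not support this, because the shrinkage is sufficient for PR. The text leaves the case undefined, and the IRC's expert reading would have to settle it.

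**The two new-node texts contradict each other.** A reader might infer that a thin new node is not PD under the Progressive Disease list. That list says that any of its items indicates PD; it does not say that nothing else does. Both texts are sufficient conditions, so together they give PD and the LPD limit is redundant. There is also another route, "New non-index disease (eg, effusions, ascites, or other organ abnormalities) of any size unequivocally attributable to lymphoma", and non-index disease covers "non-measurable evidence of lymphoma such as abnormal, non-measurable nodal lesions". That route needs unequivocal attribution, so it does not make the two node rules equal. What stands is a mismatch to harmonise, not a demonstrated wrong result.

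**The practical effect may be nil.** PET is optional, and best overall response protects anyone with a CR or PR at another scan before PD. Unscheduled scans are possible (Protocol 6.8). Appendix 6 dates progression that was uncertain and later confirmed from its first objective documentation, which may remove a shift. No formal test is planned (SAP 3.5). The IRC charter (Protocol 9.4) sets the reading methods and may already resolve both points. All of this stands and limits the size of the point.

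**Conclusion.** The main point holds on the text. With a positive baseline PET, a subject who has a ≥50% SPD fall, no new disease, a residual large-at-baseline node above 1.5 cm and a negative on-treatment PET falls in no defined category and is not counted as a responder at that scan. The same CT picture is PR with no PET or with a positive one. The new-node wording is a secondary, drafting-level mismatch.

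The size cannot be determined from the documents and may be zero. Per affected subject with no other CR or PR before PD, it is 0.83 points of ORR at n = 120 or 3.85 at n = 26.

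A reader might infer that the gap could take an arm below the 50% objective in Protocol 1.3. The documents do not establish this. At n = 120 every case shown stays above 50%. At n = 26, losing two subjects gives 46.2% from a start of 14 but 50.0% from a start of 15. Moreover, 26 is not Arm A's final size, since randomization to it continued, and Protocol 1.3 already judged Arm B unlikely to reach 50%.

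The point should be fixed because it touches a primary-endpoint definition and is cheap to settle. Confidence is moderate, since the IRC charter is unseen.

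**What to change.** Add a short paragraph to SAP section 6, and to the protocol or IRC charter if either is amended:
1. A subject who meets the other applicable PR criteria but not the CR size criterion is PR, whether the on-treatment PET is positive or negative.
2. A new node is PD if it exceeds 1.5 cm in any diameter, or if its LD is above 1.0 and up to 1.5 cm with LPD above 1.0 cm. This removes the redundant LPD limit and matches the Appendix's own definition of an abnormal node.
3. IRC response follows Appendix 6 with these two clarifications.

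Keep IRC reads already made as the primary analysis. List the affected time points: a negative PET with a residual node above 1.5 cm after a positive baseline PET, or a new node with LD above 1.5 cm and LPD of 1.0 cm or less. Report ORR, PFS and DOR under the clarified rules as a sensitivity analysis, labelled post hoc if results are already known.

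The cost is one paragraph, one listing and one sensitivity run, plus a check that the charter agrees. The listing can cover only time points where measurements were recorded; Appendix 6 does not require them for non-index lesions. Because SAP methods take precedence (SAP section 1), the SAP can carry the change without a further protocol amendment after early termination.
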